Tianjin Diabetes and Health Cohort Study

Document Date: 2025-05-07

ClinicalTrials.gov ID: NCT06913153

Research Protocol:

This study establishes a multidimensional dynamic cohort research platform leveraging comprehensive medical and healthcare data from approximately 400,000 diabetes patients in Tianjin during 2009-2023. Focused on addressing critical scientific challenges in diabetes prevention and management, the project employs advanced analytical methods to extract insights from multi-parametric data sources including electronic health records, medical imaging, and wearable device metrics.

Diabetes mellitus represents a significant global public health challenge, with its prevalence exhibiting rapid growth in China. Tianjin, serving as the medical hub of the Beijing-Tianjin-Hebei region, possesses a unique advantage through its network of secondary and tertiary hospitals that have systematically accumulated longitudinal medical data. This comprehensive dataset provides an invaluable resource for investigating the spatiotemporal patterns of diabetes epidemiology. In this study, we aim to establish a standardized data integration platform and develop innovative analytical algorithms. Leveraging the Tianjin Diabetes Population Cohort, we will construct an end-to-end research framework encompassing: disease risk prediction models, clinical decision

support systems, and health policy evaluation methodologies.

The research program comprises five synergistic modules designed to provide comprehensive insights into diabetes epidemiology.

The prevalence trends module systematically analyzes the epidemiological characteristics of diabetes and its associated risk factors, while conducting comparative studies with global datasets to establish an evidence-based foundation for researchers worldwide.

In the pathogenesis module, we will investigate the etiological mechanisms, risk factors, early biomarkers, and disease progression of diabetes mellitus and elucidate potential therapeutic targets for diabetes prevention and clinical intervention.

In the risk prediction module, we will develop advanced machine learning ensemble models to identify high-risk populations for diabetes onset, predict the critical diabetic complications including diabetic nephropathy, retinopathy progression, cardiovascular diseases, and assess the life expectancy.

In the personalized treatment and management module, we will systematically quantify the longitudinal effects of dynamic

glycemic control fluctuations on disease-specific risks and all-cause mortality, investigate medication dosing regimens and prescription patterns in relation to glycemic target achievement, and establish robust clinical evidence to standardize management protocols and optimize tiered care delivery systems for diabetes mellitus.

In the health economics module, we conducted a comprehensive evaluation of diabetes-associated health and economic burdens in Tianjin and developed disease burden trajectories models for temporal trends projection. Furthermore, we performed rigorous health economic evaluations of diabetes interventions through Markov decision-analytic modeling and microsimulation techniques to identify cost-effective diabetes management strategies.

Through the systematic integration of multi-dimensional data, this study will establish a comprehensive closed-loop research framework encompassing risk prediction, clinical intervention, and economic evaluation. This integrated approach will generate region-specific evidence to support precision diabetes prevention and control strategies in the local context.

Tianjin Diabetes and Health Cohort Study

Document Date: 2025-05-07

ClinicalTrials.gov ID: NCT06913153

Statistical Analysis Plan

Specific processes for analyzing data

1. Define the purpose of the study;
2. Identify the study population;
3. Identify intervention, exposure factors;
4. Identify outcome indicators;
5. Clean and organize data;
6. Study grouping; Missing data handling.

Statistical methods used for each analyzed item:

1. Propensity Score Matching (PSM)
2. Multivariate Parametric Proportional Hazards Model
3. Gompertz Proportional Hazards Model
4. Logistic Regression
5. Cox Proportional Hazards Model
6. Kaplan-Meier Curve
7. Autoregressive Integrated Moving Average (ARIMA) Forecasting Model
8. Bayesian Structural Time Series (BSTS) Model
9. GXboot , Support Vector Machines , Decision Trees , Random Forests
10. Health economics : Cost-Effectiveness Analysis(CAE) , Cost-Utility Analysis(CUA), Cost-Benefit Analysis(CBA)

The way key assumptions are verified:

1. Propensity Score Matching (PSM): PSM required balanced covariates ($SMD < 0.1$) and overlapping propensity score distributions for the exposed and control groups after matching. Balance will be verified by standardized mean difference (SMD), propensity score distribution plots, and between-group tests ($p > 0.05$).
2. Multivariate Parametric Proportional Hazards Model: The model assumes that the risk ratio is constant over time (proportional riskiness) and that the parameter distribution (e.g., Weibull distribution) accurately describes the time dependence. The proportional hazards assumption will first be verified by the Schoenfeld residual test ($p > 0.05$), and the goodness of fit of the model with different parameters will be compared by AIC/BIC.
3. Gompertz Proportional Hazards Model: The model assumes that the risk function follows a Gompertz distribution (exponentially varying) and satisfies proportional riskiness. The distributional assumptions will be verified by plotting the log cumulative hazard linearly versus time and comparing with other parametric models (e.g., Weibull) using the likelihood ratio test.
4. Logistic Regression : Logistic regression requires

continuous variables to be linearly related to the logit, free of multicollinearity and independent of observations. The assumption of linearity will be verified by the Box-Tidwell test, variance inflation factor (VIF<10) will be calculated to exclude multicollinearity, and data will be checked for independent samples.

11.Cox Proportional Hazards Model

12.The core assumptions of the Cox model are proportional riskiness and linear association of covariates with log risk. These two assumptions will be tested using the Schoenfeld residual test (global $p>0.05$) and Martingale residual plots, respectively.

13.Kaplan-Meier Curve

14.Kaplan-Meier analyses assumed that censoring was independent of event risk and that the mechanism of censoring was consistent between groups.Randomness of censoring will be indirectly assessed by comparing baseline characteristics of censored and non-censored subjects and by log-rank test results. If censoring is not random, data will be processed using competing risk models or multiple imputation.

15.Autoregressive Integrated Moving Average (ARIMA) Forecasting Model

16. The ARIMA model requires the time series to be smooth and the residuals to be white noise. Stationarity will be verified by the ADF test, and residual autocorrelation will be checked using ACF/PACF plots and the Ljung-Box test ($p>0.05$).

17. Bayesian Structural Time Series (BSTS) Model

18. The BSTS model assumes that the temporal structure (trend, seasonality, etc.) is well set and that the prior distribution matches the data characteristics. The model will be validated by posterior predictive checks, information criteria (WAIC/DIC), and residual normality diagnostics.

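### SAP item 1 sets a p > 0.05 balance check beside SMD < 0.1 without saying which governs, and in large matched sets the two disagree

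*SAP*

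**What the plan says.** Item 1 of the SAP's list of key assumptions (Propensity Score Matching) first states the requirement: "PSM required balanced covariates ($SMD < 0.1$) and overlapping propensity score distributions for the exposed and control groups after matching". The next sentence gives the means of checking it: "Balance will be verified by standardized mean difference (SMD), propensity score distribution plots, and between-group tests ($p > 0.05". The type of test, paired or unpaired form, matching ratio and matched-set size are not given, and neither is a rule for when the SMD and the test disagree.

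On PH, item 2 (parametric model) says: "The proportional hazards assumption will first be verified by the Schoenfeld residual test ($p > 0.05". AIC and BIC then compare parametric forms. Item 3 (Gompertz) assumes a hazard that is "exponentially varying) and satisfies proportional riskiness", but what it checks is the distribution: "The distributional assumptions will be verified by plotting the log cumulative hazard linearly versus time". Item 12 (Cox) says: "These two assumptions will be tested using the Schoenfeld residual test (global $p>0.05$) and Martingale residual plots, respectively". The last word of that sentence assigns the Schoenfeld test to PH and the Martingale plots to linearity.

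None of these items says what follows a failed check. Item 14 (Kaplan-Meier) does name a next step, but only for censoring: "If censoring is not random, data will be processed using competing risk models or multiple imputation".

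**The concern.** An SMD describes how far apart the matched groups are. A p-value combines that distance with the number of patients. With both thresholds printed side by side and no precedence, the same covariate can be balanced by one and unbalanced by the other. An analyst who applies the p-rule in a large matched set may rematch or drop patients although the SAP's own SMD requirement is met. Dropping patients also raises the p-value without improving balance, so the check can be passed for the wrong reason. In a small set the p-rule is lenient and says little about balance.

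The Schoenfeld p-value depends in the same way on the number of events. Used alone, it does not show how much the HR changes over time.

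**Working it through.** **Inputs.** From the SAP, item 1: SMD < 0.1 and p > 0.05. From the Protocol's opening paragraph: about 400,000 patients in the platform. Assumed, because the documents are silent: 1:1 matching, n per group, an unpaired two-sided test and a normal approximation. The plan has no figure of its own to reproduce.

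**Where the two rules cross.** For a standardized covariate, z = SMD / sqrt(2/n). The largest observed SMD that still passes p > 0.05 is therefore 1.96 × sqrt(2/n). Setting this to 0.1 gives n = 2 × (1.96/0.1)² = 768.3, so from 769 per group the p-rule is the stricter one. Two groups of 769 make 1,538 patients, about 0.4% of 400,000.

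**Effective SMD limit under p > 0.05:**

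| n per group | 1.96 × sqrt(2/n) |
|---|---|
| 200 | 0.196 |
| 1,000 | 0.088 |
| 5,000 | 0.039 |
| 10,000 | 0.028 |
| 50,000 | 0.012 |

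At 10,000 per group the p-rule is 0.1/0.0277 = 3.6 times stricter than the SMD rule. At 200 per group it passes almost twice the permitted SMD.

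**One covariate followed through.** An observed SMD of 0.05 meets the requirement at any size. Its z and p are:
- 1,000 per group: z = 0.05/sqrt(2/1,000) = 1.12, p = 0.26
- 5,000 per group: z = 2.50, p = 0.012
- 10,000 per group: z = 3.54, p = 0.0004

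Read in reverse, cutting the set from 10,000 to 1,000 per group turns a fail into a pass with the imbalance unchanged.

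**Sensitivity of the crossover.**
- Paired test, n = 2(1 − ρ)(1.96/0.1)²: 614.7 (615 pairs) at within-pair correlation 0.2, and 384.2 (385 pairs) at 0.5.
- 1:4 matching, unpaired, exposed n = (1 + 1/4)(1.96/0.1)² = 480.2, so 481.

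Under each alternative the conflict starts earlier.

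**PH, same mechanism.** Assume a log HR that drifts linearly over the ordered events, half of the events in exposed patients, and a 1-df test. The standard error of the end-to-end change in log HR is then sqrt(12/(events × 0.5 × 0.5)).
- 1,000 events: 0.219. The smallest estimated change reaching p < 0.05 is 1.96 × 0.219 = 0.43, an HR ratio of about 0.65.
- 40,000 events: 0.035. The smallest is 1.96 × 0.035 = 0.07, an HR ratio of about 0.93.

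The event counts are assumptions; the documents give none.

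**The case against.** **Both balance rules are mandatory.** A reader might infer this, and so conclude that the plan contradicts itself. The text does not go that far. The requirement sentence names the SMD and overlap only, and the p-value appears in a list of verification tools. A fair reading is that the SMD governs. What stands is that a pass/fail threshold is printed and the SAP does not say whether it binds.

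**The p-rule rejects everything under 0.1, or biases results.** Neither follows. Only covariates with an observed SMD between 1.96 × sqrt(2/n) and 0.1 are affected. If both checks must pass, the test can only tighten balance. The cost is lost patients, extra work or an unplanned choice; no bias in an effect estimate has been shown.

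**The Schoenfeld rule passes large drifts and fails small ones.** This holds only for a 1-df test with half the events in exposed patients. Take an HR falling from 1.50 to 1.00 at 1,000 events. It passes in 54% of analyses (1 df) or 81% (10 df: ten covariates, one drifting) at a 50% exposed share, and in 80% or 91% at a 10% share. A fall from 1.50 to 1.35 at 40,000 events is flagged in 86% or 50% at a 50% share, but in only 45% or 18% at 10%. Item 12 names the global test, so the small drift may well pass too.

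**Item 3 leaves PH unchecked.** Item 2 covers parametric PH models in general and can reasonably be read as including the Gompertz model. It remains true that item 3 names no PH check of its own.

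**Level of detail.** This is a short, platform-level SAP, and the absence of a step after PH failure is mostly missing detail. That is why the PH point is secondary.

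**Conclusion.** The concern holds as an unstated precedence between two balance checks, one of which depends on matched-set size. Under 1:1 matching with an unpaired two-sided test they conflict from 769 per group. Under the paired and 1:4 alternatives examined, they conflict from 385 to 615 pairs or 481 exposed patients. That matched sets will reach such sizes is an inference from the roughly 400,000 patients, though a strong one. The consequence is avoidable rematching or loss of patients if the p-rule is applied, and no added protection in small sets.

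The secondary point also holds: items 2 and 12 rest PH on a p-value that depends on event count, with no display of the size of the change. It is a worthwhile improvement, with less at stake on the text than the balance rule. Confidence is medium, because matched-set sizes, matching ratio and event counts are all assumed.

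**What to change.** **Item 1.** State that balance is judged by SMD < 0.1 for every covariate, together with the propensity-score overlap plots already planned. Delete the p > 0.05 threshold, or mark the between-group tests as descriptive only. This costs one clause of SAP wording. Adjusting the outcome model for residual imbalance should not be added as a matter of course. It can change a marginal HR or odds ratio into a conditional one, so it belongs in the SAP only if its effect on the estimand is stated.

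**Items 2, 3 and 12.** Keep the Schoenfeld test if wanted, but not as the sole criterion. Add smoothed scaled-Schoenfeld plots with the estimated change in log HR and its confidence interval, taken from a companion Cox fit for items 2 and 3. Define the time periods in advance, and report period-specific HRs alongside the single HR where the interval indicates a change across them. The interval should be read for the size of the change; asking only whether it excludes no change would repeat the test. The cost is a few extra plots, and what change matters remains partly a judgement.

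### SAP item 3 checks the Gompertz model with a plot that is curved under Gompertz on follow-up time, and with a likelihood ratio test against Weibull, which is not nested

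*SAP*

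**What the plan says.** Item 3 of the SAP's key assumptions (Gompertz Proportional Hazards Model) states: "The model assumes that the risk function follows a Gompertz distribution (exponentially varying) and satisfies proportional riskiness". It names two checks of the distribution, a graph and a model comparison: "plotting the log cumulative hazard linearly versus time and comparing with other parametric models (e.g., Weibull) using the likelihood ratio test".

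Item 2, directly above, covers parametric proportional hazards models and also gives Weibull as its example. There, "the goodness of fit of the model with different parameters will be compared by AIC/BIC".

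Neither document states a time scale (follow-up time or attained age), a time origin or the handling of delayed entry for any survival model. The Protocol describes data on "approximately 400,000 diabetes patients in Tianjin during 2009-2023", which limits follow-up to about 15 years.

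**The concern.** A hazard that varies exponentially in time has a log hazard that is a straight line in time. The SAP plots the log cumulative hazard instead, which is a different function and in general not straight. If time means time since cohort entry, truly Gompertz data would tend to look as if they violated the model. Weibull data are curved on the same plot, so it separates the two poorly.

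The likelihood ratio test needs one model to be a special case of the other. Gompertz and Weibull are not related in that way, so the usual chi-square p-value does not exist.

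Item 3 names no other check of the distribution. At stake is a diagnostic that can mislead and a test result that cannot validly be reported. The documents do not say which estimate the Gompertz model feeds, so no effect on a particular result is claimed.

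**Working it through.** **Inputs.** From the SAP: the Gompertz form, the plot and the test (item 3), and AIC/BIC (item 2). From the Protocol: the 2009-2023 window, about 15 years. The documents give no Gompertz parameters and no numerical result to reproduce. All values of *a* (baseline rate) and *g* (rate of increase per year) are therefore assumptions; the main range is g = 0.05 to 0.10.

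**Step 1: what is linear under Gompertz.**

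- Hazard: h(t) = a·exp(g·t), so log h(t) = log a + g·t. This is exactly linear in t.
- Cumulative hazard: H(t) = (a/g)·(exp(g·t) − 1).
- Slope of log H(t): g / (1 − exp(−g·t)). This depends on t and does not involve a.
- Under Weibull, log H is linear in log t.

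**Step 2: size of the curvature on follow-up time.** For g = 0.09:

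- year 1: 0.09 / (1 − exp(−0.09)) = 0.09 / 0.0861 = 1.046;
- year 15: 0.09 / (1 − exp(−1.35)) = 0.09 / 0.7408 = 0.121;
- ratio: 8.6.

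| g (assumed) | slope, year 1 | slope, year 15 | ratio | R² of log H on t, years 1-15 | R² of log H on log t, years 1-15 |
|---|---|---|---|---|---|
| 0.05 | 1.025 | 0.095 | 10.8 | 0.931 | 0.998 |
| 0.09 | 1.046 | 0.121 | 8.6 | 0.947 | 0.994 |
| 0.10 | 1.051 | 0.129 | 8.2 | 0.950 | 0.993 |

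The R² values are from straight-line fits on an even grid of 2,000 points. For any Weibull, log H against t over the same years gives R² = 0.907, whatever the shape. So exact Gompertz data look curved on the planned plot, only slightly less so than Weibull data, and look nearly straight on the Weibull plot. Log hazard against t gives R² = 1 for every g.

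**Step 3: attained age.** With the same g:

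- Hazard counted from birth, ages 40 to 90: the slope changes only 1.02- to 1.14-fold and R² is at least 0.9998. The planned plot then works as an approximation.
- Hazard accumulated from an assumed entry at age 40, ages 41 to 90: R² falls to 0.94 to 0.98.

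**Step 4: the likelihood ratio test.** With the same covariates, each model has two baseline parameters, so df = 2 − 2 = 0. The models share only the exponential (g = 0; Weibull shape 1). A likelihood ratio statistic for nested models cannot be negative, but this one can. In 200 simulated data sets per truth (n = 2,000, uniform censoring at 2 to 15 years):

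| Truth (assumed) | range of 2·(logL Gompertz − logL Weibull) | share negative |
|---|---|---|
| Gompertz, a = 0.02, g = 0.09 | −6.9 to 32.8 | 5% |
| Weibull, shape 1.4 | −31.5 to 10.7 | 96% |

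**Step 5: is the ranking still useful?** Yes. With equal parameter counts, AIC and BIC rank the two models by log-likelihood. In Step 4 the ranking picked the true model in 95% and 96% of data sets. In single runs at n = 200,000 with Gompertz truth (a = 0.01 to 0.02, g = 0.05 to 0.10, uniform censoring over 0 to 15 years), twice the log-likelihood difference favoured Gompertz by 256 to 1,296 units.

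**The case against.** The strongest reply has four parts.

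- **Time scale.** The SAP says only time. On attained age with hazard counted from birth, the planned plot is nearly straight. The Protocol's risk prediction module includes life expectancy, for which an age scale is plausible. This stands as a condition on the plot criticism. It does not rescue the text, because the SAP does not state that condition and the curvature returns if hazard accumulates from cohort entry.
- **Choice of window.** Curvature is greatest in the early years. With g = 0.05 to 0.10, R² against time rises to 0.974-0.983 over years 3 to 15 and to 0.988-0.993 over years 5 to 15. The SAP sets no pass mark for the plot, so saying that Gompertz data would fail is a judgement. This stands for the size of the effect, but the algebra in Step 1 holds in every window.
- **The test.** Other parametric models could include the exponential, for which the test is valid. Likelihood ratio tests for non-nested models also exist (Vuong, Cox). Both are true, but Weibull is the SAP's own example and no non-nested version is named. An unqualified likelihood ratio test normally means the nested chi-square test.
- **Consequences.** AIC/BIC would select the same model as the likelihood ranking, so only the p-value is lost. Item 2 could also be read as already covering Gompertz. This stands and limits the severity. It leaves one type of comparison with two methods in adjacent items, only one of which is valid for Weibull against Gompertz.

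**Conclusion.** The concern holds. Two statements rest on algebra alone: under Gompertz the log hazard, not the log cumulative hazard, is linear in time; and Gompertz and Weibull are not nested, so the standard test has 0 degrees of freedom.

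The size of the plot's curvature rests on assumed g of 0.05 to 0.10 per year and a follow-up scale starting at year 1. It does not apply on an age scale counted from birth.

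The harm is a misleading diagnostic and a p-value that cannot be reported. It is not an inevitable wrong choice of model, since at the full cohort size the likelihood ranking would still point to the better one. The point should be fixed before analysis.

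**What to change.** Reword item 3 as follows:

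1. State the time scale: follow-up time, or attained age with the origin and the handling of delayed entry.
2. Replace the plot by the log of a smoothed or piecewise-constant hazard against time, read for linearity.
3. Use log cumulative hazard against log time only as the Weibull check.
4. Compare Gompertz with Weibull by AIC/BIC, as in item 2, without a p-value.
5. Reserve the likelihood ratio test for nested models, for example exponential within Gompertz (g = 0, 1 degree of freedom).

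AIC/BIC repairs only the model comparison; the plot needs its own replacement. The cost is two or three sentences of SAP wording, with no data or staff cost.

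### The SAP's check for random censoring (key assumptions, item 14) cannot separate prognosis from loss to follow-up, and its remedy is not tied to endpoint or reason for censoring

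*SAP*

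**What the plan says.** The SAP's section on verifying key assumptions covers the Kaplan-Meier curve in items 13-14. It states the assumption in two parts: "Kaplan-Meier analyses assumed that censoring was independent of event risk and that the mechanism of censoring was consistent between groups". The check is: "Randomness of censoring will be indirectly assessed by comparing baseline characteristics of censored and non-censored subjects and by log-rank test results". The consequence is: "If censoring is not random, data will be processed using competing risk models or multiple imputation".

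The SAP does not define non-censored. It does not say whether the log-rank test is on event times or censoring times, and it does not distinguish death, loss to follow-up and end of data. On imputation, the list of analysis steps has only the entry "Study grouping; Missing data handling".

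The protocol covers two kinds of endpoint. The risk prediction module is to "predict the critical diabetic complications including diabetic nephropathy, retinopathy progression, cardiovascular diseases". The personalized treatment and management module studies the effects of "glycemic control fluctuations on disease-specific risks and all-cause mortality".

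**The concern.** In survival data, the non-censored are ordinarily those who had the event. Comparing them with the censored shows which baseline factors predict the event. It does not show why the others left observation. A prognostic factor will differ between the two sets even if every censoring is due to end of data. The informative contrast is between patients lost and patients still under follow-up.

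A log-rank test on event times compares event hazards between groups. It does not address the second half of the stated assumption, that censoring works the same way in each group.

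The remedy is a separate problem. Death competes with a non-fatal complication and does not compete with all-cause mortality. That follows from the endpoint, not from a test. Competing-risk methods also assume that loss is independent, so they do not repair informative loss.

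At stake is the absolute risk reported for complications. The method would be changed, or left alone, on evidence that does not answer the question asked.

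**Working it through.** The documents give no event, death or loss rate, so there is no stated figure to reproduce. All rates below are assumptions. The direction of each result follows from the algebra; the sizes depend on the rates.

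**1. Administrative censoring only.** Inputs: follow-up cut-off uniform over 15 years (2009-2023), binary factor in 50%, event hazard h = 2%/yr without it and 4%/yr with it.

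P(event) = 1 - (1 - exp(-15h))/(15h)
- h = 0.02: 1 - 0.2592/0.30 = 0.136
- h = 0.04: 1 - 0.4512/0.60 = 0.248

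Share with the factor among events: 0.248/(0.136 + 0.248) = 64.6%. Among censored: 0.752/(0.864 + 0.752) = 46.5%.

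SMD = (0.646 - 0.465)/sqrt[(0.646×0.354 + 0.465×0.535)/2] = 0.37. Kaplan-Meier is unbiased here, so the difference is prognosis alone.

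**2. Loss that depends on the same measured factor.** With loss hazard l, P(event) = integral from 0 to 15 of h·exp(-(h+l)u)·(1 - u/15) du in each stratum. Large-sample 1-KM at 7.5 years = 1 - exp(-integral of the mean hazard), with strata weighted by exp(-(h+l)u). The true 7.5-year risk is 1 - [exp(-0.15) + exp(-0.30)]/2 = 19.9%.

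| Loss per year, low-risk v high-risk | SMD, events v censored | 1-KM bias, points | Relative bias |
|---|---|---|---|
| 5% v 5% | 0.36 | 0 | 0 |
| 5% v 8% | 0.29 | -0.3 | -1.7% |
| 3% v 10% | 0.20 | -0.8 | -3.9% |
| 2% v 20% (extreme) | -0.01 | -1.9 | -9.4% |
| 8% v 5% | 0.43 | +0.3 | +1.7% |
| 10% v 3% | 0.52 | +0.8 | +3.9% |
| 20% v 2% (extreme) | 0.71 | +1.9 | +9.6% |

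The SMD shrinks as bias grows in one direction and rises with it in the other, starting from 0.36 at no bias. In 2,000 simulated runs of N = 2,000, the SAP's comparison has p<0.05 in 100%, 99.5%, 86% and 5.6% of runs for the first four rows. A log-rank test on loss times by the factor has 6.1%, 100%, 100% and 100%.

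**3. Log-rank by group.** 2,000 runs of N = 2,000, two-sided 5%:
- Loss 3% v 10%/yr by group, no group effect on events: the event-time test rejects in 5.4% of runs, the loss-time test in 100%.
- Loss 5%/yr in both, events 2% v 3%/yr: 91% and 4.7%.

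The event-time test follows the effect on events; the loss-time test follows the censoring.

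**4. Competing-risk model used as the remedy for loss.** Unmeasured factor in 50%, with event and death hazards each 1.5% without it and 6%/yr with it. Cumulative incidence = integral of exp(-H(u))·λ(u) du, where λ is the at-risk-weighted event hazard and H the cumulative total hazard. The true 7.5-year value is 19.9%. With loss of 3% v 5%/yr the estimate is off by a relative -1.8% (+1.8% if reversed). With 2% v 20%/yr, again extreme, it is off by -14.6% (+16.0%). The bias remains.

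**5. Deaths censored for a non-fatal complication.** 1-KM = 1 - exp(-ht), and cumulative incidence = h/(h+d)·(1 - exp(-(h+d)t)), at t = 7.5 years, with complication hazard h from 1% to 4% and death hazard d from 1% to 5%/yr.
- h = 1%, d = 1%: 7.2% v 7.0%, an excess of 0.3 points.
- h = 1%, d = 5%: 7.2% v 6.0%, an excess of 1.2 points and the largest relative excess (19.6%).
- h = 4%, d = 1%: 25.9% v 25.0%, an excess of 0.9 points and the smallest relative excess (3.6%).
- h = 4%, d = 5%: 25.9% v 21.8%, an excess of 4.1 points.

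Over this range 1-KM overstates risk by 0.3-4.1 points, a relative 4-20%.

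**The case against.** The SAP calls its check indirect, so it claims no proof, and independent censoring cannot be fully tested from observed data. That is fair. The difficulty lies in the next sentence, which makes further processing depend on the result.

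Non-censored might mean retained, and the log-rank test might be meant for censoring times. The text says neither, so the wording would still need to change.

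A reader might infer that the check is blind to informative loss. The figures do not support that. In the two moderate cases with higher-risk patients lost more often, it reaches p<0.05 in 99.5% and 86% of runs, and in the opposite direction the SMD rises with the bias. Only the extreme 2% v 20% case yields almost no difference for a measured driver. What stands is that the same check also flags 100% of runs with no bias, so a flag is uninformative.

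Loss driven by an unmeasured factor would also escape a model of time to loss and weighting based on it. The proposed change has no advantage there unless post-loss hazards are varied by assumption.

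A reader might also infer that Kaplan-Meier would be abandoned after a failed check. Item 14 says only that the data would be processed by other methods.

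**Conclusion.** The point holds and should be fixed. On the usual meaning of non-censored, a difference between the two sets does not indicate bias, and a smaller difference does not indicate its absence. An event-time log-rank test does not assess whether censoring is alike between groups. The remedy is mismatched because the endpoint decides whether death competes, and competing-risk models leave informative loss uncorrected.

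Under the assumed rates, bias from measured informative loss is 0.3-0.8 points in moderate cases and 1.9 in the extreme ones, in either direction. Censoring deaths for a non-fatal complication would overstate 7.5-year risk by 0.3-4.1 points.

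Confidence is high for the logic. The size is conditional, and it would go too far to conclude that the study's results will be biased. Kaplan-Meier is one of ten listed method groups, and the documents do not say which outcomes use it, how deaths are coded, or how many patients are lost.

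**What to change.** 1. Choose the estimator by endpoint. For non-fatal complications, use cumulative incidence with death as a competing event for absolute risk, and cause-specific hazards for association. For all-cause mortality, use Kaplan-Meier.
2. Replace the comparison of censored with non-censored subjects and the event-time log-rank test. Record death, loss to follow-up and end of data separately, model time to loss on covariates, and compare censoring times by group. Report these as description, not as a pass/fail trigger.
3. Do not use competing-risk models as the remedy for loss. Give a sensitivity analysis by inverse-probability-of-censoring weighting, or by multiple imputation with its variables, model and number of imputations stated. Say that it addresses only measured drivers, and add a range of assumed post-loss hazards for unmeasured ones.

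The cost is SAP wording, a definition of loss to follow-up, and some extra analysis of existing records. Reported absolute risks of complications may be lower than 1-KM would show.
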